**NCT03983434**

**October 4, 2022**

## Fecal bile acids, fecal short chain fatty acids and the intestinal microbiota in patients with irritable bowel syndrome (IBS) and control volunteers: Diet Challenge

Patients with irritable bowel syndrome (IBS) may exhibit atypical profiles of intraluminal bile acids and short chain fatty acids (SCFA). Intraluminal bile acids may influence intestinal secretion, permeability, transit, motility and visceral hypersensitivity. Bile acid sequestration, administration, and modulation of bile acid synthesis have shown promising effects on stool characteristics, colonic transit and symptoms during treatment of chronic diarrhea and constipation. Intraluminal SCFA may also exert important effects on intestinal fluid and electrolyte absorption, motility and symptoms in IBS. Altered SCFA profiles have been identified in IBS, although the pattern of these alterations is incompletely understood. Identifying the underlying mechanisms that drive differences in intraluminal bile acids and SCFA could be critical to understanding the pathogenesis of IBS.

There is emerging evidence that alterations in bile acids and SCFA associated with IBS could be associated with changes in the gut microbiota. In addition to modulating levels of intraluminal organic acids, it has been hypothesized that gut microbiota may alter local immune responses, modulate visceral pain responses, and impair gut barrier function. Our **overall goal** is to investigate the relationship between fecal bile acids, SCFA and the gut microbiota in IBS. Results of this pilot study could reveal insights into the interplay of the gut microbiota and small molecule mediators of IBS to suggest targeted clinical strategies for improved diagnosis and management of this important syndrome.

**SPECIFIC AIMS & HYPOTHESIS:** The central hypothesis of this proposal is that specific shifts in the GI microbiome composition correlate with altered colonic SCFAs and BAs and contribute to IBS symptoms

**Specific Aim 1:** Identify GI microbiome signatures in IBS subtypes (IBS-C and IBS-D) and matched controls, and test if microbiome signatures in these groups correlate with fecal SCFAs and bacterial fermentation of an indigestible carbohydrate (inulin) after a dietary challenge (fecal inulin).

**Aim 1a Hypothesis:** Abundance of specific SCFA-producing bacterial taxa (e.g. clostridial clusters IV and XIVa) correlates with fecal SCFAs and will distinguish IBS-C from IBS-D and IBS subtypes from controls.

**Aim 1b Hypothesis:** Abundance of specific SCFA-producing bacterial taxa is inversely correlated with fecal inulin and will distinguish IBS-C from IBS-D and IBS subtypes from controls.

**Specific Aim 2:** Determine if GI microbiome signatures in IBS subtypes and controls correlate with fecal BAs or markers of SCFA production (fecal SCFAs or inulin) and test if BAs correlate with fecal SCFAs or inulin.

[figure not shown]
**Aim 1b Hypothesis:** Abundance of BA-dehydroxylating taxa (e.g. genus *Clostridium*) correlates with decreased total fecal BAs in IBS-C and increased total fecal BAs in IBS-D compared to controls.

**Aim 2b Hypothesis:** Abundance of BA-dehydroxylating taxa is associated with fecal SCFAs and fecal inulin.

**Aim 2c Hypothesis:** Fecal inulin and SCFAs differ in IBS-D patients with and without BA malabsorption.

## SIGNIFICANCE

*Primary fecal BA significantly higher in IBS-D and non-secretory BA (LCA) higher in IBS-C*

Shin A et al. Clin Gastroenterol Hepatol. 2013;11:1270-1275.e1.

**Mechanistic effects of bile acids in pathogenesis of Irritable Bowel Syndrome** Despite its global prevalence and impact on quality of life, current therapeutic options and actionable biomarkers for the treatment of IBS are limited. Bile acid malabsorption is identified in up to 50% of patients with functional diarrhea or diarrhea-predominant IBS (IBS-D). Clinical studies have shown increased primary fecal bile acids, cholate and chenodeoxycholate, in IBS-D and increased non-secretory secondary bile acids, lithocholate, in constipation-predominant IBS (IBS-C). The effect of bile acids on colonic mucosa is in part, determined by bile acid chemistry. Chenodeoxycholate and deoxycholate have been

associated with increased fluid secretion, intestinal permeability and mucosal damage. Stimulation of propagated pressure waves has been shown in the proximal human colon with intraluminal chenodeoxycholate. In mice, deoxycholate induces peristalsis through TGR5-mediated effects. Administration of chenodeoxycholate or elobixibat, an inhibitor of the ileal bile acid transporter, in patients

with IBS-C and chronic constipation increases colonic transit compared to placebo. And newer farnesoid X-receptor agonists such as obeticholic acid and GW4064 are being considered for the treatment of bile acid or secretory diarrhea through attenuation of Cl secretory responses and stimulation of FGF19, an inhibitory regulator of bile acid synthesis. Meanwhile, treatment with bile acid sequestrants in IBS-D patients reduces colonic transit, improves stool consistency and improves symptoms. The rationale for targeting bile acids as a treatment for IBS arises from our growing understanding of bile acid mediated mechanisms. Altered bile acid excretion can now serve as a validated biomarker in a largely heterogeneous patient population for which targeted therapy is often challenging. However, better characterization of the mechanisms of bile acid biotransformation and the interaction between bile acids and other metabolites (e.g. SCFA) is needed to understand causes and downstream effects of altered bile acid excretion in IBS.

**Investigating the Role of the Microbiome in IBS** The strongest evidence for a direct role of the intestinal microbiota in IBS pathogenesis is the link between infective gastroenteritis and subsequent development of IBS. Numerous studies have evaluated the fecal microbial communities in IBS (reviewed in 35,36). Despite the lack of a definitive microbial signature, changes in the relative abundance of specific microbial groups among IBS patients have been recognized. Reported observations include lower biodiversity, decreased *Bifidobacterium*, increased *Veillonella*, an increased prevalence of the phylum Proteobacteria and reduced *Faecalibacterium*. Regrettably, experimental findings are also often contradictory or inconsistent, which may in part be attributable to differences in the employed experimental techniques, heterogeneous patient populations and external factors such as diet and medications. Recent emphasis has been placed on studying the functional consequences of dysbiosis in IBS and identifying microbial biomarkers associated with phenotype or symptoms such as colonic transit and clinically significant depression. Lower biodiversity in IBS has been associated with a lower abundance of butyrate-producing bacteria and methanobacteria. IBS patients have also been found to harbor higher counts of acetate and propionate-producing *Veillonella* and *Lactobacillus*. Furthermore, significant decreases in *Bifidobacterium* and *C. leptum*, organisms involved in bile salt metabolism, have been observed in IBS-D suggesting a role for microbial metabolic activity. Clarifying the functional consequences of dysbiosis through investigation of microbial communities and metabolites is needed to provide mechanistic insight into the role of the microbiome in IBS.

**Microbial Production of Short Chain Fatty Acids and their Significance in IBS** Normally, ~5-10% of all dietary complex carbohydrates is not absorbed in the small intestine and passes into the colon. Ninety percent of the starches entering the colon are fermented by colonic bacteria to SCFA of which acetate, butyrate and propionate comprise the major proportion. SCFA may stimulate intestinal transit, induce contractile responses, and promote intestinal fluid and electrolyte absorption. Intracolonic infusion of 0.5% acetic acid enhances sensitivity to colorectal distension in rats. Prior studies have shown lower levels of total SCFA, acetate, propionate and higher levels of n-butyrate in IBS-D compared to controls. In one study, significant increases of acetate and propionate were found in Japanese IBS patients, correlating with increased GI symptoms and worse quality of life. Findings suggest chemical stimuli may serve as an origin or exacerbating factor in IBS through effects on visceral hypersensitivity. In contrast, proteomic analyses of stool from IBS patients showed increased bile acids and decreased branched chain fatty acids relative to controls; however, changes in SCFA were not significant. Given conflicting results and various mechanisms by which these metabolites may affect gut physiology and symptoms in IBS, the relationship between SCFA production and intestinal microbes in IBS warrants further study.

**Relationship between intestinal microbiota and intraluminal organic acids** Bile salt hydrolases from several intestinal bacterial species including *Bacteroides*, *Clostridium perfringens*, *Bifidobacterium*, *Lactobacillus* and *Listeria monocytogenes* deconjugate bile acids. Both conjugated and deconjugated bile acids have been shown to induce intestinal secretion. Although the physiologic advantages of deconjugation are incompletely understood, there is evidence that bile salt hydrolases aid in bacterial colonization of the lower GI tract, promote detoxification of bile salts and increase resistance to bile salt toxicity. Free bile acids rapidly undergo dehydroxylation by intestinal bacteria, converting primary to secondary bile acids. This metabolic pathway is found in ~0.0001% of total colonic flora and the bacteria capable of dehydroxylation have previously been classified as *Clostridium*. Changes in fecal metabolite profiles leading bowel dysfunction and symptoms in

IBS may reflect underlying shifts in the fecal microbial community. Alternatively, alterations in underlying gut physiology such as transit may contribute to the development of dysbiosis, suggesting a bi-directional interaction. It has been hypothesized that an observed decline in anaerobes following acute gastroenteritis may be a consequence of accelerated transit resulting in a loss of the anaerobic niche, and loss of the bacteria required for carbohydrate fermentation to SCFA. Theoretically, accelerated transit may also reduce the time available for bacterial transformation of bile acids. Further investigation of the relationship between fecal microbiota and changes in the metabolome (e.g. bile acids and SCFA) is required for continued development of diagnostic and therapeutic strategies in IBS.

## INNOVATION

The utility of SCFAs as a biomarker in IBS remains uncertain. Measuring *in vivo* SCFA production in humans () is challenging. Identifying microbiome biomarkers of IBS has also been challenging due to clinical heterogeneity in patient phenotypes, technical variation in microbiome profiling methods, and inherent microbiome variability. Aims 1 and 2 of our proposal will identify factors associated with altered SCFAs in IBS by (1) **comprehensively assessing the composition of the fecal microbiota in IBS patients using deep 16S sequencing and (2) measuring SCFAs and bile acids in parallel.** In Aim 1, we will use a **novel approach to measure SCFA production** and test if SCFAs are a clinically useful IBS biomarker. Our approach is highly innovative because we will study carefully phenotyped participants and measurable pathways (SCFAs, bile acids) that could lie at the interface of IBS symptoms and the GI microbiome. We will utilize a new approach to monitor SCFA production by measuring fecal inulin in the stool. Studying the associations between bile acids and markers of SCFA production in Aim 2 is also distinctly innovative as effects of fecal bile acids on SCFA production in IBS are unknown. Our findings could generate critical preliminary data demonstrating a mechanistic pathway by which the GI microbiome is linked to IBS symptoms.

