**Statistical considerations:**

The primary endpoints for analysis will be:

- 1) Total bile acid excretion
- 2) Total and individual fecal excretion of SCFA
- 3) Fecal microbial population
- 4) Fecal inulin

The secondary endpoints for analysis will be:

- 1) Percent primary fecal bile acid excretion
- 2) Stool characteristics (frequency, consistency, ease of passage) based on bowel diary

The associations of fecal SCFAs (continuous variable) with phenotype (using HV as the reference group) and specific microbial taxa will be assessed using a general linear model (GLM) adjusting for relevant covariates. The relative abundance of specific bacterial taxa will be measured and compositional data analysis will be performed to assess the associations of relative microbial taxa abundances with fecal SCFAs or other endpoints (fecal inulin) and to assess whether phenotype alters observed associations. GLM will include specified endpoints, phenotype, the interaction between the endpoint of interest and phenotype, and relevant covariates as prediction variables for SCFAs or other endpoints of interest. False discovery rate (FDR) control will be performed using the Benjamini-Hochberg procedure to correct for multiple testing. We will explore (a) multivariable associations between overall community composition (e.g. Bray-Curtis dissimilarity) with phenotype, fecal SCFAs, or fecal inulin using the PERMANOVA approach adjusting for covariates and (b) the influence of bowel functions on the association between microbial endpoints with fecal SCFAs or inulin in IBS.

Associations of total fecal bile acids with relative abundance of microbial taxa and other specified endpoints (fecal SCFAs or inulin) will be assessed using GLM adjusting for covariates. FDR control will be performed using the Benjamini-Hochberg procedure. Among IBS-D participants, we will test associations between fecal SCFAs or inulin and bile acid phenotype (with or without bile acid malabsorption) using ANCOVA adjusting for covariates. We will explore (a) multivariable associations between overall community composition (Bray-Curtis dissimilarity) with phenotype or total fecal bile acids using the PERMANOVA approach adjusting for covariates and (b) associations between primary fecal bile acids with relative microbial abundances in IBS patients.

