**Sample size and Power:** We will enroll 24 patients with IBS-D, 24 patients with IBS-C, and 24 healthy controls. In order to compensate for withdrawals and loss to follow-up, up to 50 patients could be enrolled to meet the 24 studied in each group.

Sample size assessment is based on results of primary endpoints for Aim 1 from a preliminary dataset acquired by our lab and calculated using ANOVA among three cohort groups. We will have 80% power at the 5% significance level to detect the effect size shown in the table for fecal SCFAs between 19 IBS-C, 19 IBS-D, and 19 HV. Estimated effect sizes for other endpoints of interest are shown in the Table.

Table: Estimated effect sizes

Response (Data show mean+SD)	HV	IBS-C	IBS-D	Effect size (cohen's f)	N per group
Relative abundance of clostridial cluster IV (%)	0.181+0.221	0.392+0.354	2.01+4.06	0.39	22
Relative abundance of clostridial cluster XIVa (%)	0.0814+0.148	0.04+0.0316	0.137+0.31	0.181	99
Relative abundance of genus Clostridium (%)	0.486+0.368	0.84+0.647	2.57+3.85	0.461	16
Overall colonic transit (days)	1.55+0.977	1.52+1.39	1.08+0.649	0.461	65
Total SCFA excretion (µg/mg)	9.94+5.87	16.5+10.1	11.5+2.9	0.235	19

**Inclusion of Women, Minorities, and Children:** Individuals will not be excluded based on gender, race, or ethnicity. Patients with irritable bowel syndrome are comprised of both men and women and have diverse racial and ethnic backgrounds. The prevalence of irritable bowel syndrome among white, blacks, and Hispanics in the U.S. is very similar. Gender and racial/ethnic differences in fecal bile acid and SCFA excretion have not been reported. The communities of Marion County are anticipated to be 65% white, 29% black or African American and 6% other minorities. Children, 18-21 years of age, and adults 21 years or older will be eligible for participation in the study as active participants. However, children below 18 years of age will be excluded.

**Hazardous Procedures, Situations, or Materials and Protection of Human Subjects:** Potential exposure to radiation will be recognized. A Data Safety Monitoring Plan will be proposed. Participant records will have a unique identifier and other identifier information, including name, address, email, home address will be deleted. Only de-identified or anonymized clinical data will be transferred to processing laboratories.

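### Aim 1 is said to test whether SCFAs are a clinically useful IBS biomarker, but no planned analysis measures how well SCFA separates individuals; a significant group effect would not answer that question.

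*Combined protocol and SAP*

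**What the plan says.** The Innovation section opens by calling the value of SCFAs as a biomarker uncertain, and then says that Aim 1 will "test if SCFAs are a clinically useful IBS biomarker". The Aim 1a hypothesis also uses the language of discrimination: SCFA-producing taxa are expected to correlate with fecal SCFAs and "will distinguish IBS-C from IBS-D and IBS subtypes from controls".

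Under Statistical considerations, the analysis that links SCFA to group is a covariate-adjusted general linear model, introduced in these words: "The associations of fecal SCFAs (continuous variable) with phenotype (using HV as the reference group) and specific microbial taxa will be assessed using". The same section adds:

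- associations between taxa and SCFAs, with phenotype interactions;
- exploratory analyses of community composition "with phenotype, fecal SCFAs, or fecal inulin using the PERMANOVA approach adjusting for covariates";
- an ANCOVA of SCFAs or inulin by bile acid malabsorption status within IBS-D;
- Benjamini-Hochberg control of the false discovery rate.

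The sample size is "calculated using ANOVA among three cohort groups", with the statement "We will have 80% power at the 5% significance level to detect the effect size shown in the table" for fecal SCFAs at 19 per group. Planned enrolment is 24 per group.

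**The concern.** Whether a marker is clinically useful turns on how well it classifies individuals. Whether group means differ, or whether the marker is associated with taxa, is another question. Every planned SCFA analysis is of the second kind. The plan has no ROC curve, AUC, sensitivity, specificity, cut-off or classification model, and no criterion for usefulness.

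The plan followed exactly would therefore end with a phenotype coefficient and a p-value, and these would be the main group-level evidence bearing on the biomarker statement. If groups can differ significantly while individuals overlap heavily, that evidence does not address the stated purpose. The plan's own preliminary data show whether this is a practical risk.

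**Working it through.** **Inputs** (total SCFA row of the sample size table, µg/mg, mean and SD): HV 9.94, 5.87; IBS-C 16.5, 10.1; IBS-D 11.5, 2.9. Printed Cohen's f is 0.235 and printed N per group is 19. Planned N per group is 24, alpha 0.05.

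**Step 1. The plan's own figure.** f = SD of the group means (divisor 3) / root mean square of the group SDs.

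- Mean of means = (9.94 + 16.5 + 11.5)/3 = 12.647. Squared deviations are 7.326, 14.848 and 1.315, so the SD is sqrt(23.489/3) = 2.798.
- Root mean square SD = sqrt((34.457 + 102.01 + 8.41)/3) = sqrt(48.292) = 6.949.
- f = 2.798/6.949 = 0.403.

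Power comes from the noncentral F distribution with noncentrality 3n × f². With f = 0.403, 80% power needs 21 per group, and power at 19 is 0.76; this is close to the printed 19. With the printed f = 0.235, 80% power needs 60 per group, and power at 19 is 0.32. The printed f therefore agrees neither with its row's means and SDs nor with its row's N.

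**Step 2. Chance of a significant three-group test at 24 per group.**

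| Basis | Power |
|---|---|
| Row means and SDs, equal variances (f = 0.403, noncentrality 72 × 0.1621 = 11.67) | 0.86 |
| Row means and the stated unequal SDs, normal, simulated | about 0.79 |
| Row means and SDs, lognormal, simulated | 0.84 |
| Printed f = 0.235 (noncentrality 72 × 0.0552 = 3.98) | 0.40 |

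**Step 3. Discrimination implied by the same means and SDs.** Under a normal model, AUC = Φ(difference / sqrt(SD1² + SD2²)). The standard error is Hanley-McNeil with 24 v 24: SE² = [A(1 − A) + 23(Q1 − A²) + 23(Q2 − A²)]/(24 × 24), where A is the AUC, Q1 = A/(2 − A) and Q2 = 2A²/(1 + A).

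| Contrast | Difference / root | AUC | SE | 95% CI |
|---|---|---|---|---|
| IBS-C v HV | 6.56/11.68 = 0.562 | 0.71 | 0.075 | 0.57 to 0.86 |
| IBS-D v HV | 1.56/6.55 = 0.238 | 0.59 | 0.082 | 0.43 to 0.76 |
| IBS-C v IBS-D | 5.00/10.51 = 0.476 | 0.68 | 0.077 | 0.53 to 0.83 |

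The half-widths are 0.15, 0.16 and 0.15.

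**Step 4. Sensitivity to the assumed shape.** The documents do not give the distribution. In the same order of contrasts, the AUCs are 0.74, 0.67, 0.65 (lognormal); 0.71, 0.65, 0.64 (gamma); and 0.75, 0.56, 0.69 (normal with a common SD). All lie between 0.56 and 0.75.

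**Step 5. What an AUC of 0.71 means here.** For IBS-C v HV under the normal model, the best single cut-off is about 16 µg/mg, with sensitivity about 52% and specificity about 85%. About half of IBS-C patients would fall on the wrong side.

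**The case against.** The strongest reply is that the biomarker sentence is rationale, not a formal hypothesis. The document calls itself a pilot and expects preliminary data, and the hypothesis about distinguishing groups concerns taxa, not SCFA level. That stands as a reason to soften the sentence. It does not supply the missing analysis, because the sentence still assigns this test to Aim 1.

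Four stronger readings are tempting, and the documents do not support them.

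- *A positive trial is the expected outcome.* This holds only on the row's means and SDs. The 0.86 assumes equal variances although the SDs run from 2.9 to 10.1, and the printed f gives 0.40. The omnibus ANOVA is also the sizing tool; the planned model is covariate-adjusted with HV as reference ("The associations of fecal SCFAs (continuous variable) with phenotype (using HV as the reference group"). Pairwise power at 24 per group is about 0.79 for IBS-C v HV but about 0.21 for IBS-D v HV, so the weakest contrast would usually not be declared significant. False discovery rate control ("False discovery rate (FDR) control will be performed using the Benjamini-Hochberg procedure to correct for multiple testing") would lower these figures by an amount that the documents do not allow one to calculate, and the effect of the covariates is unknown.
- *Only mean differences are analysed.* The plan also has taxa associations, interactions, PERMANOVA and an ANCOVA. None of them measures discrimination, but the statement has to be limited to that.
- *Discrimination is poor throughout.* That fits IBS-D v HV. An AUC of 0.71 to 0.75 for IBS-C v HV is modest.
- *A significant coefficient will be reported as clinical usefulness.* Nothing in the documents says so. The plan merely offers nothing better suited to the question.

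It is also fair to object that AUCs at 24 per group cannot settle usefulness. A half-width of 0.10 would need about 52 per group at an AUC of 0.71 and about 63 at 0.58. For that reason the fix asks for preliminary estimates and sets no threshold.

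**Conclusion.** The point holds in a limited form. The plan assigns to Aim 1 a test of clinical usefulness that none of its analyses can deliver. On the table's means and SDs, a significant three-group result is more likely than not (about 0.79 to 0.86 under a normal model), and it would sit alongside AUCs of about 0.71, 0.59 and 0.68. A significant group effect would therefore not show clinical usefulness.

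This rests on total SCFA as the single marker, on the table's means and SDs rather than its printed f, on no allowance for covariates or false discovery rate control, and on an assumed distribution. The shapes tried move the AUCs within 0.56 to 0.75 and do not change the conclusion. The mismatch between stated purpose and analysis does not depend on any of these figures.

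**What to change.** Under Statistical considerations, prespecify the AUC of total SCFA with its 95% CI for three contrasts: IBS-C v IBS-D, IBS-C v HV and IBS-D v HV. Name this as the analysis that addresses the biomarker statement, and report the results as preliminary estimates. Because SCFA specimens are taken both before and after inulin, say which one is used.

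In the Innovation section, reword the sentence so that Aim 1 gives a preliminary estimate of how well SCFAs discriminate between groups, rather than a test of clinical usefulness.

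The analysis uses data already planned for every participant and changes neither recruitment nor procedures. The price is a little extra analysis and wide intervals (half-width about 0.15 to 0.16), which rule out a firm verdict on usefulness. No pass/fail bound is needed: the documents give no basis for a value, and 24 per group could seldom settle it.
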